RNA Collection (MRD Cohorts 9 and 13 to 15)

Two whole blood samples (2.5 mL per sample) will be collected predose on Day 1, predose on Day 8, and 12 hours postdose on Day 28 for RNA analysis from each subject in the study into a PAXgene tube.

RNA Collection (MRD Cohorts 10 to 12)

Two whole blood samples (2.5 mL per sample) will be collected predose donepezil on Day -21, predose TAK-071 on Day 1, and 12 hours postdose on Day 21 for RNA analysis from each subject in the study into a PAXgene tube.

RNA Collection (Cohort 16)

Two whole blood samples (2.5 mL per sample) will be collected predose on Days 1 and 42 and 12 hours postdose on Days 21 and 62 for RNA analysis from each subject in the study into a PAXgene tube.

Each PGx sample should be identifiable on the requisition form with an 8-digit subject identification number (the 5-digit site number plus the 3-digit subject number).

The samples will be stored for no longer than 15 years after completion of the TAK-071 study and/or until the drug development of TAK-071 is no longer actively pursued by Takeda or its collaborators. No samples will be stored for longer than permitted by the applicable law and samples will be destroyed upon notification from Takeda.

Detailed instructions for the handling and shipping of samples will be provided in the Laboratory Manual.

No DNA or RNA samples will be collected in Cohort 17.

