TAK-071	Plasma	28	Predose (within 30 minutes before dosing) and 0.25, 0.5, 1, 1.5, 2, 3, 4, 6, 8, 10, 12, 14, and 24 hours postdose. For Cohort 9 only, an additional sample at 36 hours postdose

Table 9.f Collection of Blood Samples for PK Analysis for Cohorts 10 to 12

Analyte	Matrix	Dosing Day	Scheduled Time (hours)
TAK-071	Plasma	1	Predose (within 30 minutes before dosing) and 0.25, 0.5, 1, 1.5, 2, 3, 4, 6, 8, 10, 12, 14, and 24 hours postdose of TAK-071
TAK-071	Plasma	8, 14, 19, and 20	Predose (within 30 minutes before dosing of TAK-071)
TAK-071	Plasma	21	Predose (within 30 minutes before dosing) and 0.25, 0.5, 1, 1.5, 2, 3, 4, 6, 8, 10, 12, 14, and 24 hours postdose of TAK-071
Donepezil	Plasma	-7, -3, and -2	Predose (within 30 minutes before dosing of donepezil)
Donepezil	Plasma	-1	Predose (within 30 minutes before dosing) and 1, 2, 3, 4, 6, 8, 10, 12, 14, and 24 hours postdose of donepezil
Donepezil	Plasma	8, 14, and 20	Predose (within 30 minutes before dosing of donepezil)
Donepezil	Plasma	21	Predose (within 30 minutes before dosing) and 1, 2, 3, 4, 6, 8, 10, 12, 14, and 24 hours postdose of donepezil

Table 9.g Collection of Blood Sample for PK Analysis of Cohort 16

Analyte	Matrix	Dosing Day	Scheduled Time (hours)
TAK-071	Plasma	1, 21, 42, and 62	Predose (within 30 minutes before dosing) and 0.5, 1, 2, 4, 6, 8, 10, 12, and 24 hours postdose of TAK-071
Donepezil	Plasma	1, 21, 42, and 62	Predose (within 30 minutes before dosing of donepezil)

Table 9.h Collection of Blood Sample for PK Analysis of Cohort 17

Analyte	Matrix	Dosing Day	Scheduled Time (hours)
TAK-071	Plasma	1 (each of 3 periods)	Predose (within 30 minutes before dosing) and 0.5, 1, 2, 3, 4, 6, 8, 10, 12, 16, 24, 32, 40, 48, 72, 96, and 168 hours postdose

Table 9.i Collection of Blood Sample for PK Analysis of Cohorts 20 to 22

Analyte	Matrix	Dosing Day	Scheduled Time (hours)
TAK-071	Plasma	1	Predose (within 30 minutes before dosing) and 2, 4, 8, 12, 16, 24, 25, 26, 27, 28, 30, 32, 36, 40, 48, 56, 64, 72, 96, and 168 hours post TAK-071 dose
Donepezil	Plasma	2	Predose (within 30 minutes before donepezil dosing) and 1, 2, 3, 4, 6, 8, 12, 16, 24, 32, 40, 48, 72, 144 hours post donepezil dose

The actual time of sample collection will be recorded on the source document and eCRF.

Sampling time points may be adjusted based on the preliminary emerging PK data collected from prior cohort(s), but the total number of samples collected per subject should not exceed the planned number.

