(a) First single dose of TAK-071.

(b) First dose of multiple daily TAK-071.

(c) Last dose of multiple daily TAK-071.

(d) Blood sample on Day 3.

(e) Blood sample on Days 9, 10, and 15.

(f) Blood samples on Days 20 and 27.

(g) Blood samples on Days 3, 4, and 5.

(h) Blood sample on Day 15.

(i) Blood sample on Days 20, 26, and 27.

(j) Blood sample at 24 hours post last dose for all 3 cohorts and an additional sample for only Cohort 9 at 36 hours post last dose.

Table 9.t Approximate Blood Volume for Cohorts 10 to 12

Sample Type	Sample Volume (mL)	Number of Samples												Total Volume (mL)	
		Screening	Day -22	Day -21 (a)	Days -10 to -2	Day -1	Day 1 (b)	Day 2	Days 3-8	Day 11	Days 12-20	Day 21 (c)	Day 22		Final Visit Day 23
Clinical laboratory tests	20	1	1	1	1 (d)	1	1	1	2 (e)	1	2	1	0	1	280
Serology test	8.5	1	0	0	0	0	0	0	0	0	0	0	0	0	8.5
PGx DNA sample collection	6	0	0	1	0	0	0	0	0	0	0	0	0	0	6
PGx RNA sample collection	2.5	0	0	2	0	0	2	0	0	0	0	2	0	0	15
PK blood collection for TAK-071	3	0	0	0	0	0	13	1	1(f)	0	3 (g)	13	1	0	96
PK blood collection for donepezil	4	0	0	0	3 (h)	10	1	0	1(f)	0	2 (g)	10	1	0	112
Total Approximate Blood Sampling Volume														517.5	

- (a) First dose of donepezil.
- (b) First dose of multiple daily TAK-071.
- (c) Last dose of multiple daily TAK-071.
- (d) A blood sample for clinical laboratory tests will be collected on Day -10.
- (e) Blood samples on Days 5, 8.
- (f) Blood sample will be collected on Day 8.
- (g) Blood samples will be collected on Days 14, 19 (TAK-071 only), and 20.
- (h) Blood samples will be collected for PK analysis of donepezil on Days -7, -3, and -2.

Table 9.u Approximate Blood Volume for Cohort 16

Sample Type	Sample Volume (mL)	Number of Samples															Total Volume (mL)
		Screening	Day -1	Day 1 (a)	Day 2	Day 11	Day 20	Day 21 (b)	Day 22	Day 41	Day 42 (c)	Day 43	Day 52	Day 61	Day 62 (d)	Final Visit Day 63	
Clinical laboratory tests	20	1	1	1	1	1	1	1	1	1	1	1	1	1	1	1	300
Serology test	8.5	1	0	0	0	0	0	0	0	0	0	0	0	0	0	0	8.5
PGx DNA sample collection	6	0	0	1	0	0	0	0	0	0	0	0	0	0	0	0	6
PGx RNA sample collection	2.5	0	0	2	0	0	0	2	0	0	2	0	0	0	2	0	20
PK blood collection TAK-071	3	0	0	9	1	0	0	9	1	0	9	1	0	0	9	1	120
PK blood collection donepezil	4	0	0	1	0	0	0	1	0	0	1	0	0	0	1	0	16
Total Approximate Blood Sampling Volume																470.5	

- (a) First dose of study drug in Period 1.
- (b) Last dose of study drug in Period 1.
- (c) First dose of study drug in Period 2.

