- (d) Last dose of study drug in Period 2.

Table 9.v Approximate Blood Volume for Cohort 17

Sample Type	Sample Volume (mL)	Number of Samples													Total Volume (mL)
		Screening	Day -1	Day 1 (a)	Days 2 to 5	Day 8	Day -1	Day 1 (b)	Days 2 to 5	Day 8	Day -1	Day 1 (c)	Days 2 to 5	Final Visit Day 8	
		Period 1				Period 2				Period 3					
Clinical laboratory tests	20	1	1	1	2 (d)	1	1	1	2 (d)	1	1	1	2 (d)	1	320
Serology test	8.5	1	0	0	0	0	0	0	0	0	0	0	0	0	8.5
PK blood collection TAK-071	3	0	0	11	6 (e)	1	0	11	6 (e)	1	0	11	6 (e)	1	162
Total Approximate Blood Sampling Volume														490.5	

- (a) Single dose of study drug in Period 1.
- (b) Single dose of study drug in Period 2.
- (c) Single dose of study drug in Period 3.
- (d) Days 2 and 5.
- (e) Three samples on Day 2 and 1 sample each on Days 3, 4, and 5.

Table 9.w Approximate Blood Volume for Cohorts 20 to 22

Sample Type	Sample Volume (mL)	Number of Samples								Total Volume (mL)	
		Screening	Day -1	Day 1 (a)	Day 2	Day 3	Day 4	Day 5	Final Visit Day 5		PK Follow-Up Day 8
Clinical laboratory tests	20	1	1	1	1	1	1	1	1	1	160
Serology tests	8.5	1	0	0	0	0	0	0	0	0	8.5
PGx DNA sample collection	6	0	0	1	0	0	0	0	0	0	6
PGx RNA sample collection	2.5	0	0	4	0	0	0	2	0	0	15
PK blood collection TAK-071	3	0	0	6	9	3	1	1	1	1	63
PK blood collection donepezil	4	0	0	0	9	3	1	1	1	1	60
Total Approximate Blood Sampling Volume										312.5	

- (a) TAK-071 dose only. Donepezil will be administered approximately 24 hours after the TAK-071 dose.

The maximum volume of blood at any single day is approximately 75 mL for Cohorts 1 to 8, and 18 to 22; 70 mL for Cohorts 9 and 13 to 15; 80 mL for Cohorts 10 to 12; 61 mL for Cohort 16; 53 mL for Cohort 17.

The approximate total volume of blood for the study is 243.5 mL for Cohorts 1 to 6, 18, and 19; 345.5 mL for Cohorts 7 and 8; 453.5 mL for Cohorts 9 and 13 to 15; 517.5 mL for Cohorts 10 to 12; 470.5 mL for Cohort 16; 490.5 mL for Cohort 17; and 312.5 mL for Cohorts 20 to 22.

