Direct venipuncture is the preferred method of blood collection; however, a catheter with a single saline flush may be used. If a catheter with a normal saline flush is used, the total blood volume does not include discarded blood from predraws (assuming minimally the catheter dead volume plus 1 mL of blood is discarded each time a sample is collected from a catheter). If a catheter is used, the total blood volume taken during the study must not exceed 550 mL for healthy subjects and 480 mL for subjects with MCI or mild AD.

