- (g) Blood and urine samples for clinical laboratory tests (hematology, coagulation, serum chemistry, urinalysis) will be collected as indicated. On Days 1 and 42, the urine sample for urinalysis will be taken at predose (within 2 hours prior to dosing) and the blood sample for these tests will be taken 1 hour postdose. On all other days, when the subjects are confined at the phase 1 unit, blood and urine samples will be taken predose upon rising in the morning under fasted condition.
- (h) FSH concentration will be obtained from postmenopausal women (defined as continuous amenorrhea of at least 2 years and not surgically sterile). The result must be >40 IU/L for the subject to be enrolled.
- (i) A standard 12-lead ECG will be recorded at Screening, Check-in (Day -1), Days 1, 21, 42, and 62 (TAK-071 predose [within 60 minutes prior to dosing] and at 0.5, 1, 2, 4, and 8 hours postdose), Days 2, 11, 20 to 22, 41 to 43, 52, and 61 to 63 (upon morning rising or arrival for outpatient visit) or ET. Single ECGs will be taken at all visits.
- (j) DIC will be dispensed for treatment.
- (k) Subjects must be receiving ongoing donepezil therapy (10 mg) in the evening for a minimum of 21 days prior to Check-in and during the study (if subjects were receiving 5 mg dose at Screening, it should be up-titrated to 10 mg on Day -21). Alternatively, subjects may be diagnosed at Screening and start donepezil run-in for 49 days prior to Day -1, and on stable 10 mg dose of donepezil 21 days prior to Day -1. Subjects will continue with their donepezil therapy during the TAK-071 Treatment Period.
- (l) Blood samples for PGx analysis will be collected as follows: 6 mL for DNA on Day 1; 2×2.5 mL for RNA predose TAK-071 on Days 1 and 42 and 12 hours postdose on Days 21 and 62.
- (m) Blood samples (3 mL/sample into EDTA coated tubes) for plasma measurement of TAK-071 will be collected predose (within 30 minutes prior to dosing) and specified time points outlined in Section 9.1.15.1.
- (n) Blood samples (4 mL/sample collected into sodium heparin tubes) for the measurement of donepezil will be collected predose (within 30 minutes prior to TAK-071 dosing) and specified time points outlined in Section 9.1.15.1.
- (o) Urine samples for PK analyses will be collected predose within approximately 1 hour of dosing and specified time points outlined in Section 9.1.15.2.

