For MRD Japanese healthy volunteer Cohorts 13 to 15, blood samples for clinical laboratory tests (hematology, coagulation, serum chemistry, urinalysis) will be collected at Screening, at Check-in (Day -1), on Days 1, 2, 3, 8, 9, 10, 15, 20, 27, 28, 29, 30 (Final Visit)/ ET and at the Follow-up Visit. On Day 1, the urine sample for urinalysis will be taken predose (within 2 hours prior to dosing) and the blood sample for these tests will be taken 1 hour postdose. On subsequent days, samples will be taken predose upon rising in the morning under fasted condition.

For Cohort 16 in subjects with MCI or Mild AD, blood samples for clinical laboratory tests (hematology, coagulation, serum chemistry, urinalysis) will be collected at Screening, at Run-in Period (Day -21), at Check-in (Day -1), on Days 1, 2, 11, 20, 21, 22, 41, 42, 43, 52, 61, 62, 63 (Final Visit)/ ET and at the Follow-up Visit. On Days 1 and 41, the urine sample for urinalysis will be taken predose (within 2 hours prior to dosing) and the blood sample for these tests will be taken 1 hour postdose. On all other days, samples will be taken predose upon rising in the morning under fasted condition.

For BA/FE Cohort 17, blood samples for clinical laboratory tests (hematology, coagulation, serum chemistry, urinalysis) will be collected at Screening and in each period at Check-in (Day -1), 30 minutes postdose on Day 1, upon rising on Days 2 and 5 and, at PK visit on Day 8 (Day 8 of Period 3 is the final visit), at ET, if occurs, and Follow-up Visit (Day 12 [±2]) of Period 3, as appropriate.

Descriptive statistics (N, mean, median, SD, minimum and maximum) of clinical safety laboratory variables will be summarized by the pooled placebo group, each TAK-071 dose level, TAK-071 overall, and overall total within each part (SRD cohorts, MRD cohorts, Cohort 16, and Cohort 17) for baseline, each postdose time point, and change from period baseline to postdose

time points in International System of Units (SI). Only the scheduled measurements will be included in the summary. No statistical tests will be performed.

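### The Cohort 16 blood-volume total omits the run-in laboratory draw listed in the SAP; with it, a run-in subject sampled by catheter would exceed the protocol's 480 mL limit by about 10.5 mL

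*Protocol*

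**What the plan says.** Protocol Section 9.5 tabulates the planned volume in "Table 9.u Approximate Blood Volume for Cohort 16". The columns go from Screening to Day -1 and on to Day 63, and none covers the run-in. The table and the text below it give the same total, "470.5 mL for Cohort 16".

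Section 9.5 prefers direct venipuncture but permits a catheter. If a catheter is used, the total taken during the study must stay within 550 mL for healthy subjects and "480 mL for subjects with MCI or mild AD". Protocol Section 9.1 has a separate ceiling of 550 mL for the case where extra safety laboratory or PK samples are taken. It gives no lower figure for patients.

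SAP Section 7.12.2 lists the Cohort 16 laboratory blood samples after Screening as "at Run-in Period (Day -21), at Check-in (Day -1), on Days 1, 2, 11, 20, 21, 22, 41, 42, 43, 52, 61, 62, 63", with early termination and the Follow-up Visit after that. Footnote (a) to the Cohort 16 schedule in Protocol Appendix A says that certain assessments apply only to subjects in the run-in. Footnote (k) places the increase to 10 mg donepezil on Day -21 for subjects who enter on 5 mg. It has newly diagnosed subjects start 49 days before Day -1 and be on 10 mg for the last 21 days. Both run-in routes therefore pass through Day -21.

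**The concern.** The run-in adds visits before Day -1, and the SAP attaches a laboratory blood draw to one of them. The blood-volume table does not count it. The unadjusted total is only 9.5 mL under the 480 mL figure, so one ordinary 20 mL laboratory draw is enough to pass it.

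The 480 mL figure is worded as a limit that must not be exceeded, and it is set lower for patients than for healthy subjects. If the draw is in the schedule, a permitted way of running the study exceeds that limit with no deviation and no unscheduled sample. The stated total would also be too low for run-in subjects. Protocol Section 13.2.1 describes Cohort 16 as still enrolling, so a correction can still take effect.

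**Working it through.** **Step 1: reproduce the stated total.** Counts and volumes are from Table 9.u, checked against the sampling sections.

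- Clinical laboratory tests: 15 × 20 mL = 300 mL.
- Serology: 1 × 8.5 mL = 8.5 mL.
- DNA: 1 × 6 mL = 6 mL.
- RNA: two 2.5 mL tubes on each of four days, 8 × 2.5 mL = 20 mL. Section 9.1.14 agrees: "predose on Days 1 and 42 and 12 hours postdose on Days 21 and 62 for RNA analysis".
- TAK-071 PK: ten samples on each of four profile days, 40 × 3 mL = 120 mL. Table 9.g agrees: "Predose (within 30 minutes before dosing) and 0.5, 1, 2, 4, 6, 8, 10, 12, and 24 hours postdose of TAK-071".
- Donepezil PK: 4 × 4 mL = 16 mL. The Appendix A footnote confirms the volume: "Blood samples (4 mL/sample collected into sodium heparin tubes) for the measurement of donepezil will be collected predose".

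Sum: 300 + 8.5 + 6 + 20 + 120 + 16 = 470.5 mL, exactly the stated figure.

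**Step 2: compare the laboratory days.** The 15 draws in Table 9.u are Screening and Days -1, 1, 2, 11, 20, 21, 22, 41, 42, 43, 52, 61, 62 and 63. The SAP list contains all of these, plus Day -21 and the Follow-up Visit. The follow-up is a telephone call unless there are abnormal findings (Protocol Section 9.3.6), so it is not counted here. Day -21 is the one planned draw that the table lacks.

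**Step 3: add the run-in draw.** The SAP gives no volume. Taking 20 mL, as for every other laboratory draw in the table:

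- Run-in total: 470.5 + 20 = 490.5 mL.
- Against the 480 mL catheter limit: 490.5 − 480 = 10.5 mL over; 10.5 / 480 = 2.2%.
- Against the 550 mL cap in Section 9.1: 550 − 490.5 = 59.5 mL under.

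**Step 4: sensitivity to the assumed volume.** 480 − 470.5 = 9.5 mL. Any Day -21 draw larger than 9.5 mL passes 480 mL, so the direction does not depend on 20 mL exactly.

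These totals count sampled blood only. Section 9.5 leaves blood discarded before catheter samples out of the total, and none is added here. The protocol also states 490.5 mL for Cohort 17; that match is a coincidence.

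**The case against.** The strongest objection is that the limit is conditional. A reader might infer that every run-in subject exceeds a safety limit. The documents do not support that: the 480 mL figure applies when a catheter is used, venipuncture is preferred, and no 480 mL limit is stated for venipuncture. For a subject sampled that way, the only other ceiling is the 550 mL in Section 9.1, and 490.5 mL is below it. This objection stands and narrows the point to catheter sampling. It does not remove the point, because the protocol expressly allows a catheter, and four profile days with ten TAK-071 samples each make its use realistic.

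Second, the draw comes from the SAP, whereas the protocol governs conduct. The text available for this check has the footnotes of the Cohort 16 schedule but not its grid, and the laboratory footnote (g) names no run-in draw. The SAP's Cohort 16 days also disagree with the protocol elsewhere. For the predose urine and 1-hour postdose blood samples, SAP 7.12.2 gives Day 41 where Appendix A gives Day 42. For postdose ECGs, SAP 7.12.4 gives Days 41 and 61 where Appendix A gives Days 42 and 62. This also stands: the draw needs confirming before the total is restated.

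Third, a reader might infer that the 9.5 mL margin means any repeat draw, such as a liver-test follow-up, breaks the limit even without the run-in. The documents do not establish this. Protocol Section 9.1.9 asks for at least six named tests and gives no volume, and it allows tests to be added to blood already drawn. Section 9.1 also has its own 550 mL ceiling for additional samples.

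Finally, the protocol calls these totals approximate and the excess is small. That bears on severity, but the limit itself is stated as a firm maximum.

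**Conclusion.** The point holds in a limited form. The 470.5 mL total is correct for a Cohort 16 subject without the run-in, but it omits a laboratory draw that the SAP lists for Day -21. If that draw is in the protocol schedule and takes 20 mL, a run-in subject's planned total is about 490.5 mL. That is 10.5 mL (2.2%) above the limit Section 9.5 sets for patients sampled by catheter.

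The conclusion rests on three conditions: the SAP's Day -21 draw is real, its volume is more than 9.5 mL, and a catheter is used. The documents also hold two ceilings with different triggers, 480 mL and 550 mL, and do not say how they fit together for Cohort 16. The excess is small, but it concerns a stated maximum for patients, and the passages should be brought into agreement.

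**What to change.** First, confirm the Day -21 laboratory draw against the Cohort 16 schedule in Protocol Appendix A. If it is confirmed, add a run-in column to Table 9.u and state the run-in total in Section 9.5 beside the 470.5 mL for other subjects (490.5 mL if the draw is 20 mL). If it is not, remove Day -21 from SAP Section 7.12.2.

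In either case, reconcile Table 9.u, SAP 7.12.2, the 480 mL catheter limit in Section 9.5 and the 550 mL cap in Section 9.1, and state which limit applies to Cohort 16 under each collection method. Which limit is right is for the sponsor and the investigator to decide.

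While the table is open, check the single-day maximum too: the Day 1 entries sum to 20 + 6 + 5 + 27 + 4 = 62 mL, against the 61 mL stated for Cohort 16.

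The cost is one table correction and a short protocol clarification, or a one-line SAP correction. No analysis changes.

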10.0 PRETREATMENT EVENTS AND ADVERSE EVENTS

10.1 Definitions

10.1.1 PTEs

A PTE is defined as any untoward medical occurrence in a clinical investigation subject who has signed informed consent to participate in a study but prior to study drug (TAK-071) administration or increase in dose/start of donepezil prior to TAK-071 dose; it does not necessarily have to have a causal relationship with study participation.

10.1.2 AEs

An AE is defined as any untoward medical occurrence in a clinical investigation subject administered a drug; it does not necessarily have to have a causal relationship with this treatment.

An AE can therefore be any unfavorable and unintended sign (eg, a clinically significant abnormal laboratory finding), symptom, or disease temporally associated with the use of a drug whether or not it is considered related to the drug.

10.1.3 Additional Points to Consider for PTEs and AEs

An untoward finding generally may:

- Indicate a new diagnosis or unexpected worsening of a pre-existing condition. (Intermittent events for pre-existing conditions underlying disease should not be considered PTEs or AEs.)
- Necessitate therapeutic intervention.
- Require an invasive diagnostic procedure.
- Require discontinuation or a change in dose of study drug or a concomitant medication.
- Be considered unfavorable by the investigator for any reason.
- PTEs/AEs caused by a study procedure (eg, a bruise after blood draw) should be recorded as a PTE/AE.

Diagnoses vs signs and symptoms:

- Each event should be recorded to represent a single diagnosis. Accompanying signs (including abnormal laboratory values or ECG findings) or symptoms should NOT be recorded as additional AEs. If a diagnosis is unknown, sign(s) or symptom(s) should be recorded appropriately as a PTE(s) or as an AE(s).

Laboratory values and ECG findings:

- Changes in laboratory values or ECG parameters are only considered to be PTEs or AEs if they are judged to be clinically significant (ie, if some action or intervention is required or if the investigator judges the change to be beyond the range of normal physiologic fluctuation). A laboratory re-test and/or continued monitoring of an abnormal value are not considered an

intervention. In addition, repeated or additional noninvasive testing for verification, evaluation or monitoring of an abnormality is not considered an intervention.

- If abnormal laboratory values or ECG findings are the result of pathology for which there is an overall diagnosis (eg, increased creatinine in renal failure), the diagnosis only should be reported appropriately as a PTE or as an AE.

Pre-existing conditions:

- Pre-existing conditions (present at the time of signing of informed consent) are considered concurrent medical conditions and should NOT be recorded as PTEs or AEs. Baseline evaluations (eg, laboratory tests, ECG, x-rays) should NOT be recorded as PTEs unless related to study procedures. However, if the subject experiences a worsening or complication of such a concurrent condition, the worsening or complication should be recorded appropriately as a PTE (worsening or complication occurs before start of study drug) or an AE (worsening or complication occurs after start of study drug). Investigators should ensure that the event term recorded captures the change in the condition (eg, “worsening of...”).
- If a subject has a pre-existing episodic condition (eg, asthma, epilepsy) any occurrence of an episode should only be captured as a PTE/AE if the episodes become more frequent, serious or severe in nature, that is, investigators should ensure that the AE term recorded captures the change in the condition from Baseline (eg “worsening of...”).
- If a subject has a degenerative concurrent condition (eg, cataracts, rheumatoid arthritis), worsening of the condition should only be captured as a PTE/AE if occurring to a greater extent to that which would be expected. Again, investigators should ensure that the AE term recorded captures the change in the condition (eg, “worsening of...”).

Worsening of PTEs or AEs:

- If the subject experiences a worsening or complication of a PTE after starting administration of the study drug, the worsening or complication should be recorded appropriately as an AE. Investigators should ensure that the AE term recorded captures the change in the condition (eg, “worsening of...”).
- If the subject experiences a worsening or complication of an AE after any change in study drug, the worsening or complication should be recorded as a new AE. Investigators should ensure that the AE term recorded captures the change in the condition (eg, “worsening of...”).

Changes in severity of AEs/serious PTEs:

- If the subject experiences changes in severity of an AE/serious PTE, the event should be captured once with the maximum severity recorded.

Preplanned surgeries or procedures:

- Preplanned procedures (surgeries or therapies) that were scheduled prior to signing of informed consent are not considered PTEs or AEs. However, if a preplanned procedure is performed early (eg, as an emergency) due to a worsening of the pre-existing condition, the

worsening of the condition should be captured appropriately as a PTE or an AE. Complications resulting from any planned surgery should be reported as AEs.

Elective surgeries or procedures:

- Elective procedures performed where there is no change in the subject's medical condition should not be recorded as PTEs or AEs, but should be documented in the subject's source documents. Complications resulting from an elective surgery should be reported as AEs.

Overdose:

- Cases of overdose with any medication without manifested side effects are NOT considered PTEs or AEs, but instead will be documented on an Overdose page of the eCRF. Any manifested side effects will be considered PTEs or AEs and will be recorded on the AE page of the eCRF.

